Serious Adverse Event Collecting and Reporting

Following the subject's written consent to participate in the study, all SAEs, whether related or not related to study drug, must be collected, including those thought to be associated with protocol-specified procedures. All SAEs must be collected that occur during the screening period and within 30

days of discontinuing dosing. If applicable, SAEs must be collected that relate to any later protocolspecific procedure (such as follow-up skin biopsy).

The investigator should report any SAE occurring after these time periods that is believed to be related to study drug or protocol-specified procedure.

An SAE report should be completed for any event where doubt exists regarding its status of seriousness.

If the investigator believes that an SAE is not related to study drug, but is potentially related to the conditions of the study (such as withdrawal of previous therapy, or a complication of a study procedure), the relationship should be specified in the narrative section of the SAE Report Form.

SAEs, whether related or unrelated to the study drug, and pregnancies must be reported to BMS within 24 hours. SAEs must be recorded on the SAE Report Form; Pregnancies on a Pregnancy Surveillance Form.

SAE Email Address: [contact]

SAE [contact]

If only limited information is initially available, follow-up reports are required. (Note: Follow-up SAE reports should include the same investigator term(s) initially reported.)

If an ongoing SAE changes in its intensity or relationship to study drug or if new information becomes available, a follow-up SAE report should be sent within 24 hours to the BMS (or designee) using the same procedure used for transmitting the initial SAE report.

All SAEs should be followed to resolution or stabilization.

SAE Reconciliation

The investigator will reconcile the clinical database SAE cases transmitted to BMS Global Pharmacovigilance (GPV&E). Frequency of reconciliation will be every three months and once prior to study database lock. BMS GPV&E will e-mail upon request from the investigator, the GPV&E reconciliation report. Requests for reconciliation should be sent to [contact]. The data elements listed on the GPV&E reconciliation report will be used for case identification purposes. If the investigator determines a case was not transmitted to BMS GPV&E, the case will be sent immediately.

Health Authority Reporting (US FDA IND)

Investigators must adhere to local Health Authority Reporting Requirements. For studies conducted under an investigator sponsored US FDA IND, provide details of the following:

- Any event that is both serious and unexpected must be reported to the Food and Drug Administration (FDA) as soon as possible and no later than 7 days (for a death or life-threatening

event) or 15 days (for all other SAEs) after the investigator's or institution's initial receipt of the information.

- BMS will be provided with a simultaneous copy of all adverse events filed with the FDA. SAEs should be reported on MedWatch Form 3500A, which can be accessed at: http://www.accessdata.fda.gov/scripts/medwatch/.

MedWatch SAE forms should be sent to the FDA at: MEDWATCH [name] Fax: [name] ([name]) http://www.accessdata.fda.gov/scripts/medwatch/

All SAEs should simultaneously be faxed or e-mailed to BMS at: Global Pharmacovigilance & Epidemiology Bristol-Myers Squibb Company [contact] Email: [contact]

Non-Serious Adverse Events

A nonserious adverse event is an AE not classified as serious.

Non-Serious Event Collecting and Reporting

The collection of non-serious adverse event (NSAE) information should begin at initiation of study drug. Nonserious adverse event information should also be collected from the start of a placebo lead-in period or other observational period intended to establish a baseline status for the subjects.

Nonserious AEs should be followed to resolution or stabilization, or reported as SAEs if they become serious. Follow-up is also required for nonserious AEs that cause interruption or discontinuation of study drug, or those that are present at the end of study treatment as appropriate.

Nonserious Adverse Events are provided to BMS via annual safety reports (if applicable), and interim or final study reports.

Laboratory Test Abnormalities

The following laboratory abnormalities should be captured and reported as appropriate:

- Any laboratory test result that is clinically significant or meets the definition of an SAE
- Any laboratory test result abnormality that required the subject to have study drug discontinued or interrupted
- Any laboratory test result abnormality that required the subject to receive specific corrective therapy.

It is expected that wherever possible, the clinical rather than the laboratory term will be used by the reporting investigator (eg, use the term anemia rather than low hemoglobin value).

Laboratory test abnormalities are provided to BMS via annual safety reports (if applicable), and interim or final study reports.

Pregnancy

If, following initiation of the investigational product, it is subsequently discovered that a study subject is pregnant or may have been pregnant at the time of investigational product exposure, including during at least 6 half-lives after product administration, the investigational product will be permanently discontinued in an appropriate manner (eg, dose tapering if necessary for subject safety).

The investigator must immediately notify [contact] of this event via the Pregnancy Surveillance Form within 24 hours and in accordance with SAE reporting procedures.

Follow-up information regarding the course of the pregnancy, including perinatal and neonatal outcome and, where applicable, offspring information must be reported on a Pregnancy Surveillance Form.

Any pregnancy that occurs in a female partner of a male study participant should be reported to BMS. Information on this pregnancy may also be collected on the Pregnancy Surveillance Form.

Protocol-required procedures for study discontinuation and follow-up must be performed on the subject unless contraindicated by pregnancy (eg, x-ray studies). Other appropriate pregnancy follow-up procedures should be considered if indicated.

Overdose

An overdose is defined as the accidental or intentional administration of any dose of a product that is considered both excessive and medically important. All occurrences of overdose must be reported as SAEs.

Other Safety Considerations

Any significant worsening noted during interim or final physical examinations, electrocardiograms, x-rays, and any other potential safety assessments, whether or not these procedures are required by the protocol, should also be recorded as a nonserious or serious adverse event, as appropriate, and reported accordingly.

c. Legal risks such as the risks that would be associated with breach of confidentiality.

There is the risk that information about you may become known to people outside this study.

d. Financial risks to the participants.

The study does not have funding to pay for any medical complications of study participation. The participants would therefore assume the potential financial risk of unanticipated medical care costs.

9. Benefits

a. Description of the probable benefits for the participant and for society. There may be no benefit to the participant. Potential benefits to society include improved knowledge about prophylaxis with oral anticoagulation medications during bariatric surgery and following surgery when treating a prior bariatric surgical patient with an oral anticoagulation medication for a medical condition such as stroke or atrial fibrillation.

10. Payment and Remuneration

a. Detail compensation for participants including possible total compensation, proposed bonus, and any proposed reductions or penalties for not completing the protocol.

To compensate patients for their time and participation - \$250.00 plus a parking pass will be given per visit completed:

Visit 1: **Pre-op**: 24 hours inpatient/48 hour blood draw outpatient/72 hour blood draw outpatient \$250.00 completed visit

Visit 2: **1 month**: 24 hours inpatient/48 hour blood draw outpatient/72 hour blood draw outpatient \$250.00 completed visit

Visit 3: **6 month**: 24 hours inpatient/48 hour blood draw outpatient/72 hour blood draw outpatient \$250.00 completed visit

Visit 4: **12 month**: 24 hours inpatient/48 hour blood draw outpatient/72 hour blood draw outpatient \$250.00 completed visit

Final Exit Interview by telephone (two weeks following visit #4): Review any adverse events that may have occurred. No compensation at this time.

The total amount of compensation possible is \$1,000.00 plus parking.

11. Costs

a. Detail costs of study procedure(s) or drug (s) or substance(s) to participants and identify who will pay for them.

No costs to the participants.

Table 3. Timeline for Study

	Year 1				Year 2			
TASK	July 2016	Oct. 2016	Jan. 2017	April 2017	July 2017	Oct. 2016	Jan. 2018	April 2018
Submission of Grant to BMS								

and Organization of Study				
Materials and supplies				
Database creation/testing				
JHU IRB approval				
Recruitment and enrollment				
Data collection				
Enter and clean data				
Data quality review				
Analyze data				
Abstract submissions				
Manuscript preparation				
Preparation of other grants				

References

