Hypothesis 2b: Patients who have recently undergone VSG surgery (1 month post-op) will have a decrease in both the Cmax and AUC, relative to pre-op values, when given a single dose of 5 mg of apixaban. The magnitude of the decrease in Cmax and AUC will be less than that seen in RYGB patients.

Rationale: Anatomic alteration of the GI tract will immediately reduce absorption in all postoperative bariatric patients. In RYGB patients, the attenuated small bowel and altered bile acid composition will lead to decreased absorption of the drug, whereas in sleeve gastrectomy patients prolonged gastric emptying may affect pharmacokinetics. These findings will be important when considering the use of apixaban as an oral anticoagulation option for perioperative VTE prophylaxis in the bariatric population, both in the acute hospital setting and after discharge in patients requiring extended VTE prophylaxis or treatment.

Hypothesis 2c: After undergoing bariatric surgery, patients at 6, and 12 months post-op will have an increase in Cmax and AUC, relative to pre-op values, when given a single dose of 5 mg of apixaban.

Hypothesis 2d: After undergoing RYGB, patients at 6, and 12 months post-op will have a greater increase in both Cmax and AUC, relative to pre-op values, than VSG patients relative to pre-op values when given a single dose of 5 mg of apixaban.

Rationale: Patients who are 6 to 12 months post-bariatric surgery generally have a 30-50% decrease in excess body weight. This decrease in body weight reduces volume of distribution of drug, potentially affecting Cmax. Results of the published Phase 1 apixaban study found that exposure to a dose of apixaban was inversely related to body weight. Therefore, we should expect higher plasma levels of apixaban in patients who are 6 to 18 months post-bariatric surgery when compared to pre-op values.

Findings of the Phase I study (3,4)

An open-label, parallel-group, non-randomized, single-dose study in healthy male and female subjects was conducted to assess the effects of body weight on the pharmacokinetics of a single 10 mg dose of apixaban. Following screening, patients were enrolled in one of three groups: low body weight (≤50kg, N=18), normal body weight (65-85kg, N=18) or high body weight (≥120kg, N=19).

Compared to normal body weight:

- There was a 27% increase in Cmax and 20% increase in AUC in patients with low body weight

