- There was a 31% decrease in Cmax and 23% decrease in AUC in patients with high body weight

The effect of RYGB vs. sleeve gastrectomy on long-term pharmacokinetics is difficult to predict because of the opposing effects of greater weight loss with reduced absorption in the RYGB patient.

These findings will be important when considering apixaban as an oral medication for long-term post-op bariatric patients who may require anticoagulation for stroke, myocardial infarction, atrial fibrillation or orthopedic procedures such as hip or knee replacements. (5, 6)

Specific Aim 3: To measure the effect of apixaban on Factor Xa activity (chromogenic anti-Xa activity assay) in bariatric surgical patients pre-operatively then at 1, 6, and 12 months post-operatively.

Hypothesis 3a: In spite of the changes in pharmacokinetics, the pharmacodynamics response (measured with a chromogenic anti-Xa activity assay) will not differ by more than 10% in comparing pre-surgical response to that at 1, 6, and 12 months after surgery.

Rationale: The changes in pharmacokinetics should not lead to a different concentrationresponse relationship in the chromogenic anti- Xa activity of individual patients following dosing with apixaban 5 mg. Were there to be a significant change in pharmacodynamics, other factors due to the altered anatomy or substantial weight loss would need to be invoked to explain that altered relationship.

3. Background (briefly describe pre-clinical and clinical data, current experience with procedures, drug or device, and any other relevant information to justify the research)

[figure not shown]
Defining Venous Thromboembolism

VTE includes both deep vein thrombosis (DVT), blood clots that form in the deep veins of the body, and pulmonary emboli (PE), blood clots that form in the deep veins of the body and then break free and enter the arteries of the lungs. VTE affects all races, ethnicities, both genders and all age groups. (1)

There is a fine balance between clot formation and fibrinolysis. Normally these two physiologic states are in dynamic equilibrium preventing patients from bleeding or clotting excessively. Numerous factors affect this delicate balance. These factors can be grouped into three broad categories, also known as Virchow's triad (after the German physician Rudolf Virchow):

- 1. Vascular injury (endothelial damage)
- 2. Activation of blood coagulation (hypercoagulability)
- 3. Venous stasis

Figure 1 Virchow's Triad

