Study population: Obese patients with a body mass index (BMI) of 35 kg/m² or greater that have been approved for bariatric surgery at the Johns Hopkins Center for Bariatric Surgery from January 2015 until all patients recruited. (See Table 3. Timeline of Study)

Consenting subjects will be hospitalized overnight in the JHBMC Clinical Research Center. A single dose of 5 mg apixaban will be administered by experienced CRU nursing staff, and blood samples for apixaban concentration and factor Xa activity will be collected before administration of the apixaban dose and at 0.5, 1, 2, 3, 4, 6, 9, 12, 18, 24, 48 and 72 hours after dosing.

The participant will be hospitalized and monitored for a 24 hour duration and then released home when they meet discharge criteria. The participant will then be asked to return back to the CRU for one blood draw at 48 hours and one blood draw at 72 hours. At hours 48 and 72 hours we will have ±4 hour window to allow for travel and check in for the participant.

The apixaban concentrations will be measured at Pfizer (all specimens will be stored and batched for shipment to a commercial laboratory), and the factor Xa activity measured at JHH under the leadership and guidance of [name] Director of the Lab. (As per [name] expertise he has recommended the *chromogenic assay* that measures factor Xa activity using reagents from Siemens.)

Dose schedule, duration, and concurrent medications:

A single dose of 5 mg of apixaban will be given at approximately one month before bariatric surgery, then 1, 6 and 12 months followingbariatric surgery. Alterations in the pharmacokinetics of the bariatric surgical patient could be due to the anatomic changes in the gastrointestinal tract, the resulting weight loss or both. By examining patients who have had undergone the surgery but have not lost adequate weight loss, we can separate the effects of these two variables. There will be no required concurrent medications. Excluded medications are strong dual inhibitors and inducers of CYP3A4 and P-glycoprotein inhibitors and inducers (see Table 2). This table has been provided by [name] who is an anticoagulant expert and co-investigator of this study.

Table 2. Excluded medications

Drug Class	Examples	Impact of co- administration	Suggested Managment	

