To determine the durability or change in pharmacokinetics and pharmacodynamics of apixaban in patients with a body mass index (BMI) of 35 kg/m² or greater following one of two bariatric surgical procedures (pre-operative versus post-operative vertical sleeve gastrectomy or Roux-en-Y gastric bypass patients).

b. Secondary outcome variables.

1. To compare/contrast the pharmacokinetics and pharmacodynamics of apixaban in bariatric surgical patients who have undergone RYGB vs. VSG.

2. To determine how the pharmacokinetics of the drug may differ when there is significant post-operative surgical weight loss (>40% estimated excess body weight) 12 months following surgery versus those patients who have suboptimal weight loss following bariatric surgery (< 40% of estimated excess body weight).

c. Statistical plan including sample size justification and interim data analysis.

We propose to study 15 subjects in each arm (RYGB vs. VSG) and use them as their own controls. We have accounted for loss to follow-up (even with a 36% (5 in each group) drop-out rate, we would have enough subjects (10 per group) to demonstrate a 36 % change in AUC with an alpha error of 0.05 and a beta error of 0.2 (Power of 80%). If there is no loss to follow-up and all patients remain in the study, this will allow us to demonstrate a 29% change in AUC with an alpha error of 0.05 and a beta error of 0.2.

These calculations were calculated based on the following data from Upreti et al.: Ratio of geometric mean point estimated for high body weight (>120 kg) vs. normal body weight for C_{max} = 0.692 (0.586, 0.818) and AUC (INF) = 0.77 (0.652, 0.912).

Routine pharmacokinetic data will be determined, including C_{max}, T_{max} and AUC for each subject at each dosing time, and compared within subjects and between subjects and between groups. Factor Xa activity will be compared to apixaban concentration at each time point.

d. Early stopping rules.

While we do not expect to have any serious adverse events related to the administration of a single dose of 5 mg of apixaban as required in this study, we will interrupt the study and report to the IRB if 10% or more of our first 12 subjects suffer a serious adverse event "definitely

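### The 6- and 12-month hypotheses are set only against pre-op, so they estimate a net effect in which lost absorption and weight loss may partly cancel; within-patient contrasts with month 1 should be added as supportive estimates.

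*Combined protocol and SAP*

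**What the plan says.** In section 2, Specific Aim 2, Hypotheses 2a and 2b predict a fall in Cmax and AUC at 1 month relative to pre-op, smaller after VSG than after RYGB. Their rationale is that "Anatomic alteration of the GI tract will immediately reduce absorption in all postoperative bariatric patients". Hypothesis 2c then states: "After undergoing bariatric surgery, patients at 6, and 12 months post-op will have an increase in Cmax and AUC, relative to pre-op values". Hypothesis 2d predicts a greater rise in RYGB patients "relative to pre-op values, than VSG patients relative to pre-op values".

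The rationale for 2c and 2d rests on weight alone. Patients at that stage "generally have a 30-50% decrease in excess body weight", and "Therefore, we should expect higher plasma levels of apixaban in patients who are 6 to 18 months post-bariatric surgery when compared to pre-op values". After the summary of the Phase 1 body-weight study, the protocol calls the long-term comparison of the procedures "difficult to predict because of the opposing effects of greater weight loss with reduced absorption in the RYGB patient".

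Section 4a, on dose schedule, attributes possible changes to anatomy, weight loss or both. It says that by studying operated patients who have not lost enough weight, "we can separate the effects of these two variables". It names no contrast.

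The primary outcome (7a) is pre-operative versus post-operative. Secondary outcome 2 (7b) splits patients at 40% excess weight loss at 12 months. Section 7c says only that Cmax, Tmax and AUC will be "compared within subjects and between subjects and between groups".

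**The concern.** On the protocol's own reasoning, surgery does two things to exposure: it lowers absorption at once, and it raises exposure later as weight falls. A 6- or 12-month value set against pre-op contains both. It can be near 1 when both effects are real, and on its own it says nothing about the size of either. The rationale for 2c does not say what has become of the absorption loss assumed in 2a and 2b. 2d predicts the greater net rise for the procedure in which 2b predicts the greater early fall.

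The design already holds a visit after the anatomic change and before most of the follow-up, with full sampling. The comparison of 6 and 12 months with that visit, in the same patient, holds the surgery itself fixed, but no hypothesis or analysis states it. The weight analysis that is stated is weaker in three ways. It dichotomises weight loss. It compares patients with one another, so it gives up the own-control design. It is also not stated to be within procedure: the protocol associates greater weight loss with RYGB, so the split is likely to be confounded with procedure, and hence with absorption.

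At stake is how the later visits can be interpreted. If 2c is not supported, the planned tests would not distinguish no effect from two opposing effects. A contrast with month 1 chosen after seeing a flat result would be post hoc.

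**Working it through.** **1. Reproduce the plan's precision.** Section 7c quotes an AUC ratio, high versus normal weight, of 0.77 (0.652, 0.912). Section 2 gives the group sizes, 18 normal and 19 high. The confidence level and sidedness are not stated; I assume a 90% interval and a two-sided 0.05 test.

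- SE of the log ratio = ln(0.912/0.652) / (2 × 1.645) = 0.102
- SD on the log scale = 0.102 / √(1/18 + 1/19) = 0.310
- SD of a within-patient difference = √2 × 0.310 = 0.439, crediting no within-patient correlation
- Paired t-test, 80% power: detectable decrease 28.9% at n=15 (plan: 29%) and 35.4% at n=10 (plan: 36%)

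The plan's figures reproduce closely, so I use 0.439 below.

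**2. Write the contrasts as ratios.** Let A be the anatomic ratio and W the full weight ratio at the later visit, and let f be the share of the log weight effect already present at month 1. If A stays constant after surgery:

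- 12 months / pre-op = A × W
- 1 month / pre-op = A × W^f
- 12 months / 1 month = W^(1−f)

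Only the last is free of A.

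**3. Range of the net contrast.** Reversing the protocol's weight contrast in full gives W = 1/0.77 = 1.30. This is an upper bound: it moves a patient from the ≥120 kg group to the 65–85 kg group, whereas the protocol expects only part of the excess weight to be lost. If the log effect is proportional to excess weight lost (an assumption), a 30–50% loss gives W = 1.30^0.3 = 1.08 to 1.30^0.5 = 1.14. I take W from 1.10 to 1.30. The documents give no figure for A; I assume 0.77 to 0.90.

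- Lowest product: 0.77 × 1.10 = 0.85
- Highest product: 0.90 × 1.30 = 1.17

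Exact cancellation needs A = 1/W: an absorption loss of 23% for W = 1.30, or 12% for W = 1.14.

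**4. Power of each contrast** (paired t, two-sided 0.05, SD of difference 0.439; the pooled column assumes the same effect in both procedures):

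| Contrast | Ratio | n=15 | n=30 pooled |
|---|---|---|---|
| vs pre-op, W=1.30, A=0.85 | 1.10 | 13% | 22% |
| vs pre-op, exact cancellation | 1.00 | 5% | 5% |
| vs month 1, W=1.30, f=0 | 1.30 | 58% | 88% |
| vs month 1, W=1.30, f=0.2 | 1.23 | 41% | 71% |
| vs month 1, W=1.30, f=0.4 | 1.17 | 25% | 47% |
| vs month 1, W=1.14, f=0 | 1.14 | 19% | 35% |

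With 10 completers in a group, power for a ratio of 1.30 is 39%. For the RYGB-versus-VSG difference in change after month 1, the SE with 15 per group is 0.439 × √(1/15 + 1/15) = 0.160. Within one group it is 0.439/√15 = 0.113. The 2d comparison is therefore less precise still.

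**5. Why f may not be zero.** By Table 1 the first dose is 3–5 weeks before surgery and the second 4–6 weeks after it, so they are 3+4 = 7 to 5+6 = 11 weeks apart. The documents give no body weight at month 1, so f is unknown.

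**The case against.** The strongest reply is that the net contrast is the right one. The abstract asks how dosing may need to change between pre- and post-surgery, and the primary outcome matches that. If the effects cancel, net exposure has not risen and rejecting 2c is correct. This stands, and it is why the pre-op contrasts should be kept.

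Second, the information is already implied. Among completers, the log 12-month/1-month ratio is the 12-month/pre-op log ratio minus the 1-month/pre-op log ratio. A fall at month 1 beside a flat month 12 would suggest recovery to any careful reader, and the wording of 7c does not exclude the contrast. This also stands: what is missing is the pre-stated estimate and its interval. A reader might infer that the trial must fail in its purpose. The documents do not support that, because the data permit the analysis and separating the mechanisms is a remark in section 4a, not a Specific Aim.

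Third, secondary outcome 2 does examine weight among operated patients. It does, with the weaknesses given above; it should be supplemented, not ignored.

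Fourth, month 1 is not pure anatomy. A reader might infer that using it as reference separates the two effects cleanly. It does so only approximately: weight may already have fallen by then, and later gut adaptation would count as a weight effect.

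Fifth, a null result against month 1 could also be ambiguous at this sample size. That is true, and is a reason to present estimates with intervals as supportive.

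**Conclusion.** The concern holds as a gap between what section 4a says the design can do and what sections 2 and 7 plan to estimate. All of 2a to 2d and the primary outcome refer to pre-op, the protocol itself posits opposing effects, and the one stated weight analysis is a dichotomised between-patient split likely to be confounded with procedure.

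The net 12-month/pre-op AUC ratio spans about 0.85 to 1.17 under the assumed inputs. A reader might infer that the pre-op contrast is bound to come out flat. One can choose pairs that nearly cancel (0.77 × 1.30 = 1.00), but the full range runs from a 15% fall to a 17% rise, A has no source in the documents, and W = 1.30 is an upper bound. Cancellation is possible, not expected.

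The added contrast improves interpretation but does not secure power. All power figures rest on reading the quoted interval as a 90% interval and on a constant anatomic effect after surgery. The change is worth making because it is cheap and uses planned visits.

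**What to change.** 1. Keep the pre-op contrasts, with 2c as worded, and label them as tests of net exposure.
2. Add to 7c, as supportive estimates with confidence intervals, the within-patient contrasts of 6 and 12 months versus 1 month in log AUC and log Cmax, by procedure and pooled.
3. Add to 7c a within-patient model of log AUC and log Cmax with a post-surgery indicator by procedure plus body weight at each dosing visit, to supplement the 40% split.
4. State 2d's weight-loss prediction for RYGB versus VSG as the change after month 1.
5. State the limits: month 1 may already include some weight loss; the post-surgery indicator absorbs any other change that starts at surgery; late gut adaptation loads onto the weight slope; and precision is limited, most of all for the comparison of procedures.

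The cost is a few sentences in sections 2 and 7c and a body weight recorded at each of the four dosing admissions. No visits, samples or patients are added. The downside is a few more estimates to report, which is why they should be labelled supportive.
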